#### Secondary endpoints

##### 1. Presence of Transthyretin amyloid (ATTR) or patients with suspicion of MGUS / Light Chain Amyloidosis (AL)

- Patients with grade 2 or 3 at scintigraphy will be considered “Cardiac amyloidosis patients”
  - Patients with grade 2 or 3 at scintigraphy without monoclonal protein abnormalities will be considered patients with **ATTR amyloidosis**
  - Patients with grade 2 or 3 at scintigraphy with monoclonal protein abnormalities will be considered of the population of **patients with suspicion of MGUS or AL amyloidosis**
- Patients with grade 1 at scintigraphy will be considered as “**undetermined**”

Monoclonal protein abnormalities are defined as patients with positive IFE (Immunofixation electrophoresis) (serum and urine) or with abnormal FLC (free light chain) ratio:

	eGFR			
	>60	45-<60	30-<45	<30
Abnormal FLC ratio	≥1.65	≥1.92	≥2.06	≥2.17
Normal FLC ratio	<1.65	<1.92	<2.06	<2.17

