**Figure 1. Diagnostic Algorithm for Patients with Suspected Amyloid Cardiomyopathy (Gillmore 2016)**

Echocardiographic features suggesting/indicating cardiac amyloid include (but are not limited to) increased left ventricular wall thickness, restrictive filling pattern, abnormal left and right ventricular longitudinal strain, and atrial septal thickening.

Features suggesting/indicating cardiac amyloid on cardiac magnetic resonance imaging (CMR) include (but are not limited to) restrictive morphology, abnormal gadolinium kinetics, and extracellular volume expansion based on T1 mapping.

AApoA1 indicates apolipoprotein A-I; DPD, 3,3-diphosphono-1,2-propanodicarboxylic acid; HDMP, hydroxymethylene diphosphonate; and PYP, pyrophosphate.

Moreover, the data clearly indicate that the combined finding of grade 2 or 3 cardiac uptake on radionuclide scintigraphy and the absence of a monoclonal protein by serum immunofixation electrophoresis (IFE), urine IFE, and sFLC (Freelite) assay was 100% specific for presence of ATTR-CM (Gillmore 2016).

A diagnosis of ATTR-CM should be followed by TTR genotyping in all patients to differentiate between wild-type and variant ATTR-CM.

The main purpose of this study is to determine the prevalence of ATTR-CM among patients admitted due to LVH of unknown etiology when radionuclide bone scintigraphy or SPECT is used.

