#### **9.2.4. Blood Samples Analyses**

Following the standard practice guidelines for the patient population with positive scintigraphy, blood and urine analyses are usually done to rule out AL amyloidosis. If performed, results of these tests will be collected.

Moreover, to differentiate between wild-type and variant ATTR-CM, genotyping are usually completed. If performed, results will be collected.

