#### **Full Analysis Set 3 – All FAS2 patients with positive scintigraphy grade 2 or 3 (Cardiac amyloidosis)**

Full Analysis Set 3 (FAS3) is a subset of FAS2 patients with grading of cardiac retention equal to grade 2 or grade 3.

**FAS 3.1** Patients with grade 2-3 **without** monoclonal protein abnormalities (ATTR amyloidosis)

**FAS 3.2** Patients with grade 2-3 **with** monoclonal protein abnormalities (Undefined etiology, cardiac ATTR amyloidosis, or MGUS or AL Amyloidosis). Monoclonal protein abnormalities if defined as Positive IFE (serum and/or urine) or positive FLC (See definition in section 6.3).

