### **7 HANDLING OF MISSING VALUES**

Missing data will not be imputed.

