### 2) Impact of protocol amendment 2 – No longer using a centralized lab

The prevalence of patients with laboratory signs will be calculated in patients included before protocol amendment and in patients included after protocol amendment (Amendment 2 – Date: 11-Feb-2020). The percentage and its 95% CI will be provided.

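### The SAP has no class for grade 2-3 patients whose monoclonal protein work-up is missing or incomplete, so the ATTR set (FAS 3.1) and its prevalence depend on an unstated choice

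*SAP*

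**What the plan says.** SAP 6.3, secondary endpoint 1, gives the rule: "Patients with grade 2 or 3 at scintigraphy without monoclonal protein abnormalities will be considered patients with" ATTR amyloidosis. Grade 2-3 patients with an abnormality go to the group with suspected MGUS or AL, and grade 1 is undetermined. The abnormality is defined by positive findings alone: "Monoclonal protein abnormalities are defined as patients with positive IFE (Immunofixation electrophoresis) (serum and urine) or with abnormal FLC (free light chain) ratio". SAP 5.1 makes the same two-way split of FAS3 into FAS 3.1 (without) and FAS 3.2 (with). SAP 8.2 reports the prevalence of ATTR and of suspected MGUS/AL in FAS1.

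The tests are not mandatory. Protocol 9.2.4 says of patients with a positive scan that "blood and urine analyses are usually done to rule out AL amyloidosis. If performed, results of these tests will be collected", and Protocol 9.2.2 collects laboratory results where available. Amendment 2 deleted biological sample collection. The SAP's sensitivity analysis headed "No longer using a centralized lab" examines laboratory signs only, not the ATTR classification.

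The protocol's rationale (section 7) rests the non-biopsy diagnosis on grade 2 or 3 uptake combined with "the absence of a monoclonal protein by serum immunofixation electrophoresis (IFE), urine IFE, and sFLC (Freelite) assay was 100% specific" for ATTR-CM. The abstract likewise limits reliable diagnosis to patients evaluated for monoclonal gammopathy and found free of it.

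On missing values, SAP 7 says only "Missing data will not be imputed". SAP 8.1 refers percentages to non-missing data.

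**The concern.** A patient with grade 2-3 uptake and no IFE or sFLC result has no positive finding, so under a literal reading is without an abnormality and enters FAS 3.1. The same holds for a patient with one negative test and two not done. The label would then rest on the scan alone, for which Protocol 7 quotes about 87% specificity, against 100% with the negative work-up. Less testing would yield more ATTR and less suspected AL.

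Elsewhere the SAP does ask for an actual result: ATTRwt needs a sequencing report without mutation, and absence of CTS needs a recorded negative answer. The monoclonal rule has no such condition.

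Both documents name ATTR-CM prevalence as the study's main purpose. FAS 3.1 also carries the symptom and family-history descriptions, and the SAP has no other ATTR definition for the ATTR-CM comparison and regression in SAP 8.2. ATTRv and ATTRwt are subsets of ATTR patients and inherit the problem, but only for patients who have been sequenced.

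**Working it through.** **Planned precision.** Protocol 9.5 assumes 10% prevalence, N = 1500 and a 95% two-sided interval. The half-width is 1.96 × √(0.10 × 0.90 / 1500) = 1.52 points, which reproduces the stated ±1.5.

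**Assumptions.** The documents give neither the share of grade 2-3 patients with incomplete work-up (u) nor the share abnormal when tested (m). I take grade 2-3 as 10% of FAS1, that is G = 150 of 1500, and vary u and m. For simplicity, incomplete patients have no abnormal result on file.

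**Spread between the extremes.** Counting all incomplete patients in FAS 3.1, or none, with FAS1 as denominator, changes its share by 0.10 × u:
- u = 10%: 1.0 point
- u = 20%: 2.0 points
- u = 30%: 3.0 points

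The spread equals 1.5 points at u = 0.015 / 0.10 = 15%.

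**Three readings at m = 20%.** Tested and negative = G(1 − u)(1 − m). With every patient fully tested and the same m throughout, the FAS 3.1 share would be 150 × 0.80 / 1500 = 8.0%.

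| u | Incomplete counted as ATTR | Out of numerator only | Out of numerator and denominator |
|---|---|---|---|
| 10% | (108 + 15)/1500 = 8.2% | 108/1500 = 7.2% | 108/1485 = 7.3% |
| 20% | (96 + 30)/1500 = 8.4% | 96/1500 = 6.4% | 96/1470 = 6.5% |
| 30% | (84 + 45)/1500 = 8.6% | 84/1500 = 5.6% | 84/1455 = 5.8% |

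At u = 20% the literal reading is 0.4 point above 8.0%. The missing-data reading (last column) is 1.5 points below it: the 30 dropped patients are all scan-positive, while grade 0 and grade 1 patients, classified by grade alone, stay in the denominator.

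**Patients in 3.1 who would belong in 3.2.** This is G × u × m. At u = 20%, 150 × 0.20 = 30 are incomplete. With m from 10% to 25%, 3 to 7.5 of them (about 3 to 8) would have shown an abnormality: 3/1500 = 0.2 point to 7.5/1500 = 0.5 point.

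**The case against.** The strongest reply is that the SAP nowhere says untested patients are ATTR. Treating an absent test as negative is in effect imputing a negative, which SAP 7 appears to rule out, and SAP 8.1 reports missing counts and bases percentages on non-missing data. This stands: a reader might infer that the SAP expressly assigns the untested to ATTR, and the documents do not support that. It does not close the gap, because the SAP does not choose between the readings and the missing-data reading brings its own understatement.

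Other points that stand in part:
- Testing is described as usual practice, and Protocol 9.9.3 expects monitoring and e-CRF warnings to limit losses after the scan. The untested share may be small; it is unknown.
- The table shells are only examples, and the column for all of FAS3 would expose a remainder outside 3.1 and 3.2. That would reveal the problem without resolving it.
- SAP 5.1 allows that FAS 3.2 may contain cardiac ATTR. A patient in 3.1 who belongs in 3.2 is therefore not shown to lack ATTR.
- The formal primary endpoint is grade 1-3 fixation, and all tests are exploratory. This limits the severity.

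**Conclusion.** The classification of untested and partly tested grade 2-3 patients is undefined. The literal wording sends them to ATTR, against the protocol's own diagnostic basis; the missing-data reading understates the FAS 3.1 share of FAS1. With grade 2-3 assumed in 10% of FAS1, the choice moves that share by up to 1.0 point for each 10% incompletely worked up, reaching the planned ±1.5 points at about 15%.

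The 1 to 3 points at 10-30% incomplete are a spread between two classification extremes. A reader might take them as bias, but the documents give no untested share from which a bias could be estimated. The number placed in 3.1 instead of 3.2 is smaller: about 3 to 8 of 150, or 0.2 to 0.5 point, at 20% untested and 10-25% abnormal.

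The FAS 3.1 descriptions and ATTR-CM comparisons are affected; the primary endpoint is not. This should be fixed, but it does not undermine the study's primary result.

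**What to change.** In SAP 5.1 and 6.3:
- Define FAS 3.1 as grade 2-3 with serum IFE, urine IFE and sFLC all available and none abnormal.
- Keep FAS 3.2 as grade 2-3 with any abnormal result, and align the IFE wording, which is serum and/or urine in 5.1 but serum and urine in 6.3.
- Add FAS 3.3: grade 2-3, no abnormal result, work-up incomplete. Report its count and give it a column in the FAS 2&3 version of Table 15.1.2. State that an sFLC ratio lacking the creatinine needed for the eGFR-specific cut-off counts as incomplete when it cannot be classified.
- Keep the full FAS1 as denominator.
- Report FAS 3.1/FAS1 and (FAS 3.1 + FAS 3.3)/FAS1 as the range for the proportion meeting the non-biopsy ATTR definition. Do not present these as bounds on true ATTR prevalence, since FAS 3.2 may contain ATTR.

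The cost is SAP wording, one derived category and one table column, with no new data. The downside is a smaller FAS 3.1 and a range in place of one figure.

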Gillmore analyses of 374 patients with EMBs, corroborated in the whole cohort of 1,217 patients, indicate that cardiac uptake (grade 1, 2, or 3) on a radionuclide bone scan is >99% sensitive but not completely specific for cardiac ATTR (68% specificity compared with EMB histology); the low specificity results largely from low-grade uptake in patients with cardiac AL or cardiac apolipoprotein A-I amyloidosis (*Hutt 2014*). The specificity for cardiac ATTR of grade 2 or 3 cardiac uptake on radionuclide imaging increases to ≈87%, but the sensitivity falls to 91%. Because it is absolutely essential to avoid misdiagnosis of cardiac ATTR in a patient who actually has cardiac AL requiring chemotherapy, the primary aim of the proposed diagnostic criteria was to achieve very high diagnostic specificity. The specificity and positive predictive value for ATTR-CM of the combination of grade 2 or 3 cardiac uptake on a radionuclide scan and the absence of a detectable monoclonal protein despite serum immunofixation electrophoresis (IFE), urine IFE, and serum free light chain (sFLC) assay were 100% (positive predictive value confidence interval, 99.0–100%) in this cohort of 1,217 patients and were also 100% among each of the 3 different radiotracer cohorts. Although we acknowledge that further validation of 99mTc-HMDP scintigraphy against EMB histology is required, the presented preliminary data for 99mTc-HMDP indicate that it behaves identically to 99mTc-DPD and 99mTc-PYP.

The diagnosis of ATTR-CM is often delayed or missed as a result of the poor sensitivity and specificity of ECHO (*Kristen 2010*), coupled with the current requirement for histological confirmation of amyloid in a tissue biopsy. The diagnosis of ATTRwt is particularly challenging because it presents in older age (when confounding comorbidities such as coronary heart disease, hypertension, and aortic stenosis frequently coexist) (*Pinney 2013, Gillmore 2016*).

[figure not shown]
Bone scintigraphy enables the diagnosis of ATTR-CM to be made reliably without the need for histology in patients who do not have a monoclonal gammopathy. Non-invasive diagnostic criteria for ATTR-CM are applicable to the majority of patients with this disease (*Gillmore 2016*).

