### 3. Description of variables of interest

Variables of interest are all variables collected in the CRF (including Kappa, Lambda, IgG, IgA and IgM rates from monoclonal protein studies).

- Variables of interest will be described in the FAS2 & 3 population in patients with 1, 2 or 3 redflags.
- Variables of interest will be described in the FAS1 population in patients with grade 0/1/2/3.
- Variables of interest will be described in the FAS2 & 3 population in patients with ATTRv and ATTRwt.

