## 11 APPENDICES

### 11.1 APPENDIX 1: DATA DERIVATION DETAILS

Age = (Patient screening visit date – Birthdate + 1) /365.25 , where day of birth is imputed to 15, as only month and year of birth are recorded.

Diastolic Blood Pressure classes:

- < 60 mmHg,
- [61 – 70] mmHg,
- [71 – 80] mmHg,
- [81 – 90] mmHg,
- [91 – 100] mmHg,
- > 100 mmHg.

Heart Rate classes:

- < 50 bpm,
- [51 – 60] bpm,
- [61 – 70] bpm,
- [71 – 80] bpm,
- [81 – 90] bpm,
- [91 – 100] bpm,
- [101 – 120] bpm,
- > 120 bpm.

PR interval classes:

- [90 – 100] ms
- [101 – 110] ms
- [111 – 120] ms
- [121 – 130] ms
- [131 – 140] ms
- [141 – 150] ms
- [151 – 160] ms
- [161 – 170] ms
- [171 – 180] ms
- [181 – 190] ms
- [191 – 200] ms
- [201 – 210] ms
- [211 – 220] ms
- [221 – 230] ms

- [231 – 240] ms
- [241 – 250] ms
- [251 – 260] ms
- [261 – 270] ms
- [271 – 280] ms
- > 280 ms

Serum Free Light Chain Ratio:

sFLC Ratio = Kappa / Lambda,

sFLC ratio classes:

- < 0.26,
- [0.26 – 1.65],
- > 1.65.

Abnormal values for all quantitative variables will be defined after medical advise.

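### The SAP's free light chain rule has no lower limit, so a marked lambda excess counts as normal and the patient is labelled ATTR; the IFE condition is also worded in two different ways

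*SAP*

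**What the plan says.** SAP 6.3 (Other endpoints, secondary endpoint 1) divides grade 2-3 patients by whether they have a monoclonal protein abnormality. Those without one are ATTR amyloidosis; those with one are suspected MGUS or AL. The condition is: "Monoclonal protein abnormalities are defined as patients with positive IFE (Immunofixation electrophoresis) (serum and urine) or with abnormal FLC (free light chain) ratio". The table below it calls the ratio abnormal at or above 1.65, 1.92, 2.06 or 2.17, depending on eGFR. The row labelled "Normal FLC ratio" covers everything below those values and has no floor.

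SAP 5.1 (Full Analysis Set 3) uses the same split to form FAS 3.1 and FAS 3.2, but words it differently: "Monoclonal protein abnormalities if defined as Positive IFE (serum and/or urine) or positive FLC". It refers to 6.3 for the definition.

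SAP Appendix 1 (11.1) states "sFLC Ratio = Kappa / Lambda" and lists three classes: below 0.26, 0.26 to 1.65, and above 1.65. It ends with a general line: "Abnormal values for all quantitative variables will be defined after medical advise".

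Protocol 9.3 lists serum IFE and urine IFE as separate variables. Protocol 7 rests the non-biopsy diagnosis of ATTR-CM on grade 2-3 uptake with no monoclonal protein on serum IFE, urine IFE and the serum free light chain assay.

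**The concern.** With kappa in the numerator, a kappa excess gives a high ratio and a lambda excess a low one. The 6.3 table detects only the first. Appendix 1 shows that the SAP's authors regarded very low ratios as a distinct range, but the diagnostic rule does not use it.

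The IFE wording raises a second, conditional problem. With two separate results per patient, the program needs a combination rule, and the SAP gives two.

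At stake is the purity of the group labelled ATTR. Protocol 7, describing the cited diagnostic criteria, says "it is absolutely essential to avoid misdiagnosis of cardiac ATTR in a patient who actually has cardiac AL requiring chemotherapy", and the missing lower limit errs in that direction. The rule feeds:

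- the secondary prevalence of ATTR versus suspected MGUS/AL, reported in FAS1;
- every FAS 3.1 and FAS 3.2 column;
- the ATTRv and ATTRwt results, including those reported in FAS2 and FAS3, because both labels are defined only among ATTR patients;
- the ATTR-CM comparison and regression (SAP 8.2, Other analyses 4 and 6), to the extent that ATTR-CM is taken to mean FAS 3.1, which the SAP does not state.

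**Working it through.** **1. The plan's own figures, as a yardstick.** Protocol 9.5 assumes 10% prevalence and N=1500. The half-width is 1.96 × √(0.10 × 0.90 / 1500) = 0.0152, which matches the stated ±1.5 points. For a 30% sign in 150 patients, 1.96 × √(0.30 × 0.70 / 150) = 0.0733, which matches ±7.3. At N=1000, the minimum named in the amendment table, 1.96 × √(0.10 × 0.90 / 1000) = 0.0186.

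**2. Two mirror-image patients, both grade 2-3 with both IFEs negative.**
- Kappa 20 times lambda: ratio 20, at or above the limit in every eGFR band, so abnormal and FAS 3.2.
- Lambda 20 times kappa: ratio 1/20 = 0.05, below every limit, so normal and FAS 3.1 (ATTR). Section 5.1 gives the same label because it takes its definition from 6.3.

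**3. All patterns with complete tests.** There are two results for each IFE and three ratio ranges (below 0.26; middle; at or above the eGFR-specific limit), so 2 × 2 × 3 = 12. Each cell shows the label under literal 6.3 / under 5.1 / under a two-sided rule that accepts either fluid, with 0.26 as the lower limit.

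| IFE | Ratio below 0.26 | Middle | At or above limit |
|---|---|---|---|
| Both negative | ATTR / ATTR / 3.2 | ATTR / ATTR / ATTR | 3.2 / 3.2 / 3.2 |
| Serum only positive | ATTR / 3.2 / 3.2 | ATTR / 3.2 / 3.2 | 3.2 / 3.2 / 3.2 |
| Urine only positive | ATTR / 3.2 / 3.2 | ATTR / 3.2 / 3.2 | 3.2 / 3.2 / 3.2 |
| Both positive | 3.2 / 3.2 / 3.2 | 3.2 / 3.2 / 3.2 | 3.2 / 3.2 / 3.2 |

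Patterns labelled ATTR: 6 / 2 / 1. The two faults separate as follows.
- *Missing lower limit.* With 5.1's IFE wording it mislabels one pattern (both IFEs negative, ratio below 0.26). With literal 6.3 it acts in three (the low-ratio cells of the first three rows). A lower limit only enlarges the abnormal set, so leaving it out can only enlarge ATTR.
- *IFE wording.* Literal 6.3 and 5.1 differ in four patterns, all ATTR under 6.3. If 5.1 is followed, this fault adds none.

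These are logical patterns, not patient frequencies.

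**4. Scale.** One relabelled patient moves ATTR prevalence by 100/1500 = 0.07 points, or 100/1000 = 0.10 points. The documents give no rate for either pattern, so the following is assumption. Take 150 grade 2-3 patients (10% of 1500, borrowing the protocol's ATTR-CM figure).
- Low ratio with both IFEs negative in 0-10%: 0-15 patients, or 0-1.0 points (15/1500).
- If literal 6.3 is also programmed and a further 0-10% are positive in one fluid with a ratio below the cut-off: 0-30 patients in total, or 0-2.0 points (30/1500), against 1.52.

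The relative effect on FAS 3.2 is larger. If FAS 3.2 is 10-20% of 150 (15-30 patients, assumed), five relabelled patients, an arbitrary number, would be 5/30 to 5/15, or 17-33% of it.

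**5. Boundaries.** An eGFR of exactly 60 falls in no column of the table, which matters only if eGFR is rounded. A ratio of exactly 1.65 with eGFR above 60 is abnormal in 6.3 but in the middle class of Appendix 1.

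**The case against.** The strongest reply is that Appendix 1 leaves abnormal values to medical advice, so a lower limit could still be set. That is a general statement about all quantitative variables. For this ratio 6.3 already gives explicit numbers, and a programmer would follow them.

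On IFE, the words in 6.3 can be read as naming the two fluids tested; 5.1, which forms the analysis sets, would then settle the matter. This is a fair reading, although the SAP does not say so. A reader might infer that both faults necessarily inflate ATTR; the documents support that only for the missing lower limit.

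A reader might also infer that no correction could move a patient into ATTR. That is not strictly so: if the 1.65 boundary is settled on Appendix 1's side, a patient at exactly that value with eGFR above 60 and negative IFE moves into ATTR.

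Nor do the documents make 0.26 an established diagnostic limit. It is a descriptive class boundary, it does not vary with eGFR as the upper limits do, and nothing says whether it should.

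Finally, a relabelled patient is not necessarily a missed AL case. SAP 5.1 allows that FAS 3.2 may itself contain ATTR, and these are analysis labels in a non-interventional study. The protocol's warning about AL concerns clinical diagnosis; here it shows only which direction of error matters.

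**Conclusion.** The missing lower limit is a real error in a stated rule, and it holds under either IFE wording. It can only add patients to ATTR. The IFE mismatch is a second inconsistency whose effect depends on which section is programmed: four patterns of 12 if 6.3 is taken literally, none if 5.1 is followed.

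The number of patients cannot be derived and may be small, since the low-ratio gap under 5.1 also requires both IFEs to be negative. The 0-1.0 and 0-2.0 point ranges rest wholly on assumed rates. The pattern count assumes complete tests, whereas Protocol 9.2.4 collects results only if the tests were performed; how partly tested patients are classified is a separate question.

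The primary endpoint (grade 1-3 uptake) does not use this rule, and SAP 4.2 calls all tests exploratory. This should be fixed before analysis, but it does not threaten the main result.

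**What to change.** Reconcile SAP 5.1, 6.3 and Appendix 1 into one definition, for analysis labels only, and use it throughout:

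- IFE positive in serum, urine or both (the 5.1 rule, consistent with Protocol 7); or
- a kappa/lambda ratio outside a two-sided range, keeping the eGFR-specific upper limits and adding a lower limit. The SAP's own 0.26 is the natural candidate. The medical review foreseen in Appendix 1 should confirm it, including whether it should vary with eGFR, and it should be fixed before analysis.

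Also assign an eGFR of exactly 60 to a band, put 1.65 on the same side in 6.3 and Appendix 1, and state whether ATTR-CM in SAP 8.2 means FAS 3.1.

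The cost is SAP wording and a few lines of derivation. No new data are needed: serum and urine IFE and creatinine are listed in Protocol 9.3, and SAP 8.2 counts the light chains among the CRF variables ("including Kappa, Lambda, IgG, IgA and IgM rates from monoclonal protein studies"), all where performed. The downside is a slightly smaller FAS 3.1 with slightly less precise estimates.
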